	
 8. Willingness by subject to be randomized to receive either ofatumumab or duvelisib at the dose and schedule defined in the protocol 9. Must meet the following laboratory parameters: 
 a. Serum aspartate transaminase (AST/SGOT) or alanine transaminase (ALT/SGPT) ≤ 3 x upper limit of normal (ULN) b. Total bilirubin ≤ 1.5 x ULN c. Serum creatinine ≤ 2.0 x ULN d. Hemoglobin ≥ 8.0 g/dL with or without transfusion support e. Platelet count $\geq 10,000$ μL with or without transfusion support 10. For women of childbearing potential (WCBP): negative serum β-human chorionic gonadotropin (βhCG) pregnancy test within 1 week before randomization (WCBP defined as a sexually mature woman who has not undergone surgical sterilization or who has not been naturally post-menopausal for at least 24 consecutive months [women ≤ 55 years] or 12 consecutive months [women > 55 years]) 11. Willingness of male and female subjects who are not surgically sterile or postmenopausal to use medically acceptable methods of birth control from the first dose of study drug to 30 days after the last dose of duvelisib and for 12 months after last dose of ofatumumab. Sexually active men, and women using oral contraceptive pills, should also use barrier contraception 12. Ability to voluntarily sign consent for and adhere to the entire study visit schedule and all protocol requirements 13. Signed and dated institutional review board (IRB)/independent ethics committee (IEC)-approved informed consent form (ICF) before any study specific screening procedures are performed

Exclusion Criteria:
	
Subjects are to be excluded from the study if they meet any of the following criteria:
 
 1. History of Richter's transformation or polymphocytic leukemia 2. Autoimmune hemolytic anemia (AIHA) or idiopathic thrombocytopenic purpura (ITP) that is uncontrolled or requiring > 20 mg once daily (QD) of prednisone (or equivalent) to maintain hemoglobin > 8.0 g/dL or platelets $> 10,000$ μL without transfusion support

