1.3.2.2 Study IPI-145-02 (Phase 1, Hematologic Malignancies)

Study IPI-145-02 is a Phase 1, open-label, dose-escalation study of duvelisib administered orally twice daily during each 28-day cycles at doses ranging from 8 mg BID to 100 mg BID in adult subjects with advanced hematologic malignancies. Enrollment in all phases of the study is complete, with follow-up ongoing. As of 08 October 2014, 210 subjects received at least one dose of duvelisib including 55 subjects with relapsed/refractory CLL/SLL (8 mg [n=1]; 15 mg [n=2]; 25 mg [n=28]; 75 mg [n=24]). The median time on treatment for all relapsed/refractory subject doses was 5.9 months (range 0.9 to 34.1 months), and 7.6 months (range 0.9 to 34.1 months) for doses \leq 25 mg.²⁰

The maximum tolerated dose (MTD) was determined to be 75 mg BID based upon two dose limiting toxicities (DLTs) experienced by two subjects receiving 100 mg BID (Grade 3 rash and Grade 3 alanine aminotransferase [ALT]/aspartate aminotransferase [AST] elevations). Six expansion cohorts were enrolled at 25 mg BID or 75 mg BID to further define the safety and efficacy of duvelisib in select diseases. The 25 mg dose was selected for phase 3 development based on clinical activity.²¹

Clinical Safety in Relapsed/Refractory CLL/SLL

Frequently occurring (\geq 20% subjects) AEs observed in all relapsed/refractory CLL/SLL subjects (n=55) included neutropenia (53%), rash (combined terms) (46%), diarrhea (44%), cough (38%), fatigue (38%), pneumonia (combined terms) (36%), ALT/AST increased (29%), anemia (29%), pyrexia (27%), nausea (26%), decreased appetite (24%), and thrombocytopenia (22%). Serious adverse events occurring in more than 1 relapsed/refractory CLL/SLL subject included pneumonia (combined terms) (15 [27%]), febrile neutropenia (8 [15%]), diarrhea (3 [5%]), constipation (2 [4%]), hypercalcemia (2 [4%]), pyrexia (2 [4%]), and stomatitis (2 [4%]).²⁰

These events are not unexpected based on the patient population and the mechanism of action of duvelisib. Infection prophylaxis and dose modifications included in the IPI-145-07 protocol are intended to reduce the risk of the frequently occurring events.

Clinical Efficacy in Relapsed/Refractory CLL/SLL

As of 08 October 2014, 52 subjects overall with relapsed/refractory CLL/SLL and 30 subjects who received duvelisib \leq 25 mg BID with relapsed/refractory CLL/SLL had available efficacy data.

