4.2 DOSE INTERRUPTION/HOLD/MODIFICATION GUIDELINES

4.2.1 Duvelisib Guidelines

Duvelisib treatment will consist of 25 mg administered orally BID continuously for up to 18 cycles. Duvelisib may be continued beyond 18 complete cycles, if the subject meets the criteria for additional treatment at Cycle 19 Day 1 (see [Section 4.2.1.2](#)). Duvelisib dosing may be modified due to benefit or toxicity as described below.

4.2.1.1 *Duvelisib treatment modification guidelines due to duvelisib-related toxicities*

Subjects will be monitored continuously for toxicity while on study treatment. Toxicity will be assessed using the National Cancer Institute Common Terminology Criteria for Adverse Events (NCI CTCAE) Version 4.03. If a subject has an AE at least possibly related to duvelisib, then dose interruptions/holds with possible modifications as described below in [Table 8](#) may be implemented. Deviations from these guidelines may occur based on the clinical judgment of the Investigator with notification to the Medical Monitor/Sponsor. There should be no attempt to make up for missed doses of duvelisib.

Table 8: Dose Interruption/Hold/Modifications for Duvelisib-Related Toxicities

Duvelisib-related Toxicities ^{a, b}	Dose Interruption/Hold/Modification/Recommendation for Duvelisib ^c

Nonhematologic: Grade 2 or higher Pneumonitis/Pneumonia Or Grade 3 or higher other Nonhematologic
	
First occurrence: Withhold until return to ≤Grade 1 or baseline level; re-challenge therapy at original dose level. Second occurrence of the same AE: Withhold until return to ≤Grade 1 or baseline level; re-initiate therapy at one dose level lower from current dose.

Hematologic: Grade 3 or higher febrile neutropenia Or Grade 3 or higher thrombocytopenia with Grade ≥2 hemorrhage.
	
Third occurrence of the same AE: Withhold until return to ≤Grade 1 or baseline level; re-initiate therapy at one dose level lower from current dose. Fourth occurrence of the same AE: Discontinue subject from study drug

Recommendations for implementing duvelisib dose interruptions
 
Immediate hold for Grade 4 or higher nonhematologic toxicity and Grade 3 or higher febrile neutropenia. For all other events, reduce from BID dosing to QD for two days, then hold.
	

- a. Duvelisib-related toxicity = possible, probable, or definite relationship to duvelisib as defined in [Section 8.2.1](#).

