- b. Toxicity grades are defined per CTCAE Version 4.03. Note if parameter is not defined by CTCAE, then AE grading criteria ([Section 8.2.1](#)) should be utilized.
- c. Refer to [Table 9](#) for duvelisib dose levels.

Treatment Interruption for Nonhematologic Toxicity

Treatment with duvelisib should be interrupted for the following nonhematologic toxicities:

- Grade 2 or higher pneumonitis/pneumonia, defined as symptomatic and requiring medical intervention, including oral antimicrobials and/or steroids
 - Subjects who develop new pulmonary symptoms (eg, cough, shortness of breath, dyspnea on exertion) or new radiographic findings should have duvelisib held and receive empiric antimicrobial coverage while undergoing evaluation. Corticosteroids for symptomatic treatment of pneumonitis is recommended (and allowed per protocol). Restarting treatment with duvelisib is allowed after complete resolution of symptoms.
- Grade 3 or higher other nonhematologic toxicity including the following:
 - Infections: Subjects who develop infections requiring IV antibiotics/antifungals/anti-virals should have duvelisib held until infection resolves (subject may restart duvelisib when completing a course of oral therapy). Prophylaxis to prevent recurrence/opportunistic infections will not preclude the subject from restarting treatment.
 - Hepatic events: Subjects who develop Grade 3 or higher transaminase (ALT/AST) elevations with or without clinical symptoms should have duvelisib held until return to baseline. Additional work-up to evaluate viral infection/re-activation, exposure to environmental toxins (eg, alcohol/con-meds), or other causes is recommended before restarting treatment with duvelisib.

- **Gastrointestinal:** Subjects who develop Grade 3 or higher nausea, vomiting or diarrhea despite optimal treatment should have duvelisib held until resolution of symptoms. Evaluation of concomitant medications, gastrointestinal infections or inflammatory bowel (via endoscopy and biopsy) should be considered with persistent diarrhea or recurrence with restarting duvelisib. Corticosteroids (budesonide) with taper are allowed if colitis is suspected/cannot be ruled out.

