8.2.3.2 Immediate Reporting of Medical Events of Interest

Reports or laboratory results of **AST or ALT > 3x ULN in combination with total bilirubin > 2x ULN are medical events of interest**, and therefore immediately reportable events, even if the events do not meet serious adverse event criteria.

Clinical findings of **Grade 3 or higher rash are medical events of interest**, and therefore immediately reportable events, even if the events do not meet serious adverse event criteria. Pre-existing skin conditions that recur would not meet this definition unless the recurrence is of a greater severity/frequency than previously experienced.

All medical events of interest will be reported to the Sponsor or designee within 24 hours of the Investigator's first knowledge of the event, even if the experience does not appear to be related to study drug. Medical Events of Interest should be communicated on the SAE / Medical Events of Interest (MEOI) report form, as described above for SAEs.

Any occupational exposure or exposure of an individual not enrolled in the study to the investigational medicinal product must be reported to the Sponsor or designee within 24 hours of the Investigator's first knowledge of the event, even if the exposure does not result in an adverse event. Unintentional exposures should be communicated on the SAE/MEOI report form, as described above for SAEs.

8.2.3.3 Reporting of Serious Adverse Events to the Institutional Review Board (IRBs)/ Ethics Committee

Verastem or designee shall notify the Investigator and/or the IRBs/ECs per institutional guidelines of potential serious risks from clinical trials or any other sources, including the following:

- Suspected adverse reaction that is both serious and unexpected.
- Any findings from other studies that suggest a significant risk in humans exposed to the drug.
- Any finding from animal or in vitro testing that suggest a significant risk to humans exposed to the drug, such as mutagenicity, teratogenicity, or carcinogenicity; or report of significant organ toxicity at or near the expected human exposure.

Verastem or designee shall notify Central Ethics Committees (CEC) of new serious, related, and unexpected AE(s) or significant risks to subjects, per country requirements.

The Investigator will notify Local Ethics Committees (LECs) of serious, related and unexpected AE(s) or significant risks to subjects, per local country requirements.

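### Inclusion criterion 9a joins AST and ALT with *or*; read literally, one enzyme within 3 x ULN satisfies it and the other has no numeric cap

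*Protocol*

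**What the plan says.** Criterion 9a in the protocol synopsis reads "Serum aspartate transaminase (AST/SGOT) or alanine transaminase (ALT/SGPT) ≤ 3 x upper limit of normal (ULN"). The matching bullet in Section 5.1.1 has the same wording, again "Serum aspartate transaminase (AST/SGOT) or alanine transaminase (ALT/SGPT") at the same limit, so the body does not settle what the synopsis leaves open. The next item is a separate cap: "Total bilirubin ≤ 1.5 x ULN". No section says that both transaminases must be within the limit.

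Three other parts of the protocol use the same enzymes:

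- **Reporting (Section 8.2.3.2).** The immediately reportable liver event is "AST or ALT > 3x ULN in combination with total bilirubin > 2x ULN".
- **Hold and restart (Section 4.2.1.1).** The hepatic text says "Subjects who develop Grade 3 or higher transaminase (ALT/AST) elevations with or without clinical symptoms should have duvelisib held until return to baseline". Table 8 in the same section gives a different restart condition: "Withhold until return to ≤Grade 1 or baseline level". The re-evaluation text after the organ-specific list also accepts either Grade 1 or baseline.
- **Known toxicity (Section 1.3.2.2).** The dose-limiting toxicities at 100 mg BID were "Grade 3 rash and Grade 3 alanine aminotransferase [ALT]/aspartate aminotransferase [AST] elevations". ALT/AST increase was reported in 29% of 55 relapsed/refractory CLL/SLL subjects.

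In the SAP, Section 7.3.2 plans a shift table from baseline grade to maximum post-baseline grade, and a listing of subjects with raised ALT or AST together with bilirubin above 2 x ULN.

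**The concern.** An entry limit on a laboratory value exists so that sites need not rely on judgment for that value. With *or* between the enzymes, 9a can be applied at about 100 sites in two ways, and one of them leaves a transaminase unlimited. The drug under test has documented transaminase toxicity, and the protocol manages it by comparing later values with baseline.

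If a subject comes in with one enzyme already at Grade 3, three things weaken together. The restart condition can be satisfied at a Grade 3 value. Under Section 8.1.1 a pre-existing condition becomes an adverse event only if it worsens. The shift table starts from a high grade. Under the literal reading such an entry is also not a protocol deviation, so the deviation summary in SAP Section 7.1.2 need not show it.

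**Working it through.** The plan states no figure on this point, so the check is one of logic. AST, ALT and bilirubin are in multiples of ULN.

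**1. The conditions.**

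- 9a, one enzyme suffices: AST ≤ 3 or ALT ≤ 3. This fails only when both exceed 3.
- 9a, each enzyme: AST ≤ 3 and ALT ≤ 3.
- 9b: bilirubin ≤ 1.5.
- Reporting rule, transaminase part: AST > 3 or ALT > 3.
- Reporting rule in full: the transaminase part and bilirubin > 2.

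The negation of (AST > 3 or ALT > 3) is (AST ≤ 3 and ALT ≤ 3). The entry condition that mirrors the reporting rule's transaminase part is therefore the each-enzyme version, which 9a does not plainly state.

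**2. Worked cases.** The documents refer to CTCAE 4.03 for grades and give no ULN multiple for Grade 3. Three cut-offs are assumed to show the range: > 3, > 5 and > 8.

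| AST | ALT | Bilirubin | 9a and 9b, one suffices | 9a and 9b, each | Transaminase part of reporting rule | Full reporting rule | Grade 3 if cut-off > 3 / > 5 / > 8 |
|---|---|---|---|---|---|---|---|
| 2 | 2 | 1.5 | pass | pass | no | no | no / no / no |
| 2 | 4 | 1.5 | pass | fail | yes | no | yes / no / no |
| 2 | 6 | 1.5 | pass | fail | yes | no | yes / yes / no |
| 4 | 4 | 1.5 | fail | fail | yes | no | yes / no / no |
| 6 | 6 | 1.5 | fail | fail | yes | no | yes / yes / no |

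Only discordant subjects (rows 2 and 3) change between the two readings. Since the second enzyme has no ceiling under the literal reading, some value of it passes 9a and is Grade 3 whatever the true cut-off.

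**3. Can the full reporting rule be met at entry?** It needs bilirubin > 2, and 9b requires ≤ 1.5; the two cannot both hold. A grid of AST and ALT from 0.5 to 20 and bilirubin from 0.5 to 3.0 found no combination that passes entry and meets the full rule.

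**4. Restart wording with a Grade 3 baseline.** For a subject with a normal baseline, the hepatic text asks for return to baseline while Table 8 also accepts Grade 1. For a subject whose baseline is Grade 3, both are satisfied at Grade 3. The hepatic text also speaks of subjects who develop Grade 3 elevations and does not say how it applies to someone who arrived there.

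**5. Toxicity context.** The 29% is 0.29 x 55 ≈ 16 subjects. The 55 were dosed at 8 mg (1), 15 mg (2), 25 mg (28) and 75 mg (24), so 24/55 = 44% received three times this trial's starting dose.

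**The case against.** The strongest reply is that this is an ambiguity, not a stated policy. Criterion 9 is a list of parameters that must be met, and its first item can be read as applying the limit to whichever enzyme is tested. That reading is available. It is not secure, because Section 8.2.3.2 and SAP Section 7.3.2 both use *or* between these two enzymes to mean that either one is enough.

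Second, meeting 9a is not the same as being eligible. Exclusion 16 lets the investigator exclude for an abnormal laboratory finding judged to raise risk, and exclusions 12 and 13 remove hepatitis B or C, alcohol abuse and chronic liver disease. These safeguards are real, but none sets a number. Exclusion 13 does not cover an isolated transaminase rise and exempts metastatic disease to the liver.

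Third, the analysis effect is modest. A shift table displays baseline grade, so high-baseline subjects are visible, and randomization should spread them over both arms. This stands. The loss is in the room to show worsening within those subjects, not in the fairness of the comparison.

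Fourth, the toxicity evidence is not specific to 25 mg BID. The dose-limiting event was at 100 mg BID and the 29% pools all doses. This also stands.

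A reader might infer two stronger things that the documents do not support. One is that such a subject is already at the reporting level on entry; 9b rules that out. The other is that such a subject would appear in the SAP's ALT/AST plus bilirubin listing with no on-study change. The listing uses treatment-emergent values and needs bilirubin above 2 x ULN within 2 days of the transaminase elevation, so bilirubin must first rise from 1.5 x ULN or less.

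**Conclusion.** The concern holds as a wording gap in a numeric safety criterion. Read literally, 9a leaves one transaminase uncapped, and a subject at the Grade 3 hold level can meet it, subject only to investigator judgment. For that subject the restart wording gives no real recovery target and the baseline-to-worst-grade shift can show little.

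This rests on two things: that some sites would follow the literal reading, and that some screened subjects have enzymes on opposite sides of 3 x ULN. The documents give no frequency for either, so no count of affected subjects can be offered. That a hold-level value can pass does not depend on which multiple of ULN defines Grade 3. Sample size, power, alpha and the efficacy endpoints are untouched. The change is worth making because it is cheap and bears on safety, not because it threatens the trial's conclusions.

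**What to change.** Reword 9a identically in the synopsis and Section 5.1.1 so that the sponsor's existing 3 x ULN limit unambiguously covers AST and ALT each. If the sponsor does intend one enzyme to suffice, say so explicitly. Then reconcile the wording with the transaminase condition in Section 8.2.3.2 and with the hold and restart text in Section 4.2.1.1, where the hepatic paragraph, Table 8 and the re-evaluation text do not state the same condition. Which restart condition applies is for the sponsor to decide; no new limit or clinical rule is proposed here.

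The cost is a text edit and a few more screen failures. Both enzymes are already measured at Screening under Section 6.2.1, so no procedure is added. If enrolment has closed, a short listing of subjects whose two baseline enzymes fall on opposite sides of 3 x ULN, by arm, would show whether the ambiguity mattered.

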Figure 2: Steady State Exposure (AUC₀₋₁₂) Versus Response (Reduction in Adenopathy) in CLL/SLL Subjects (Study IPI-145-02; preliminary data)41

Figure 3: Duvelisib (IPI-145) Plasma Concentration Versus Tumor Cell pAKT Inhibition Following a Single Dose in CLL/SLL Subjects (Study IPI-145-02; preliminary)41

Figure 4: Mean Duvelisib (IPI-145) Plasma Concentration-Time Profiles on Cycle 2, Day 1 (Study IPI-145-02; preliminary data).....42

LIST OF ABBREVIATIONS AND DEFINITIONS OF TERMS

Abbreviation	Definition
ADL	Activities of daily living
ADME	Absorption, distribution, metabolism, and excretion
AE	Adverse Event
AIHA	Autoimmune hemolytic anemia
ALC	Absolute lymphocyte count
ALT	Alanine aminotransferase
ANC	Absolute neutrophil count
aPTT	Activated partial thromboplastin time
AKT (PKB)	A serine/threonine protein kinase
ASCO	American Society of Clinical Oncology
AST	Aspartate aminotransferase
AT	All Treated
AUC	Area under the curve
BBB	Bundle branch block
β hCG	β human chorionic gonadotropin
BID	Twice a day
BTK	Bruton's tyrosine kinase
BUN	Blood urea nitrogen
CAL-101	Idelalisib (GS-1101): a PI3K- δ inhibitor in clinical development for patients with hematologic malignancies
CBC	Complete blood count
CD20	B-lymphocyte antigen CD20
CEC	Central Ethics Committee
CI	Confidence interval
CLL	Chronic lymphocytic leukemia
cm	Centimeters
C _{max}	Maximum concentration
CNS	Central nervous system
CMV	Cytomegalovirus
CO ₂	Chloride bicarbonate

Abbreviation	Definition
CR	Complete response
CRi	Complete response with incomplete marrow recovery
CT	Computed tomography
CTCAE	Common Terminology Criteria for Adverse Events
CYP	Cytochrome P450
d	Day
DDI	Drug-drug interaction
Del(17p)	Deletion of the 17p13 chromosomal region
dL	Deciliter(s)
DLT	Dose limiting toxicity
DMC	Data monitoring committee
DNA	Deoxyribonucleic acid
DOR	Duration of response
Duvelisib (IPI-145)	(S)-3-(1-(9H-purin-6-ylamino)ethyl)-8-chloro-2-phenylisoquinolin-1(2H)-one
EBV	Epstein-Barr virus
ECOG	Eastern Cooperative Oncology Group
ECG	Electrocardiogram
eCRF	Electronic case report form
EMA	European Medicines Agency
ESMO	European Society for Medical Oncology
EQ-5D	EuroQol – 5D (health-related QoL assessment)
ETT	Early treatment termination
EU	European Union
FACIT-F	Functional Assessment of Chronic Illness Therapy-Fatigue
FACT	Functional Assessment of Cancer Therapy
FcεRI	High-affinity IgE receptor
FCγRII	Fc fragment of IgG, low affinity IIa, receptor (CD32)
FDA	Food and Drug Administration

Abbreviation	Definition
FISH	Fluorescence in situ hybridization
FMLP	N -formyl-leucine-methionine-phenylalanine
g	Gram(s)
GCP	Good Clinical Practice
G-CSF	Granulocyte-colony stimulating factor
GM-CSF	Granulocyte macrophage-colony stimulating factor
GPCR	G-protein coupled receptor
GRAS	Generally regarded as safe
GS-1101	Idelalisib (see CAL-101)
h	Hour(s)
HBcAb	Hepatitis B core antibody
HBsAg	Hepatitis B surface antigen
HCV Ab	Hepatitis C virus antibodies
HIV	Human immunodeficiency virus
HSV	Herpes simplex virus
IC ₅₀	Half maximal inhibitory concentration
IC ₉₀	90% inhibitory concentration
ICF	Informed consent form
IDMC	Independent Data Monitoring Committee
IEC	Independent Ethics Committee
Ig	Immunoglobulin
IGHV	Immunoglobulin heavy chain variable
in	inches
INR	International normalized ratio
IRB	Institutional Review Board
IRT	Interactive Response Technology
ITP	Idiopathic thrombocytopenic purpura
ITT	Intent-to-treat
IV	Intravenous(ly)
IWCLL	International Workshop on Chronic Lymphocytic Leukemia
IWG	International Working Group

Abbreviation	Definition
K _d	Dissociation constant
kg	Kilogram(s)
KPS	Karnofsky Performance Status
L	Liter(s)
LDH	Lactate dehydrogenase
LEC	Local Ethics Committee
LLC	Lewis lung carcinoma
MedDRA	Medical Dictionary for Regulatory Activities
MEOI	Medical Events of interest
mg	Milligram(s)
μg	Microgram(s)
μL	Microliter(s)
mL	Milliliter(s)
μM	Micromolar
MRD	Minimum residual disease
MRI	Magnetic resonance imaging
ms	Millisecond(s)
MTD	Maximum tolerated dose
N	Number
NCCN	National Comprehensive Cancer Network
ng	Nanogram(s)
nM	Nanomolar
Ofa	Ofatumumab
ORR	Overall response rate
OS	Overall survival
pAKT	Phosphorylated AKT
PCR	Polymerase chain reaction
PD	Progressive disease
PE	Physical exam
PET	Positron emission tomography
PDK-1	3-phosphoinositide dependent protein kinase-1

Abbreviation	Definition
PE	Physical examination
PFS	Progression-free survival
P-gp	P-glycoprotein
PH	Pleckstrin homology
PI3K	Phosphoinositide-3-kinase
PIP3	Phosphatidylinositol (3,4,5)-trisphosphate
PK	Pharmacokinetics
pM	Picomolar
PML	Progressive multifocal leukoencephalopathy
PR	Partial response
PRwL	Partial response with lymphocytosis
PT	Prothrombin time
PTEN	Phosphatase and tensin homolog
QD	Once a day
QoL	Quality of life
QTcF	QT interval corrected with Fridericia's method
RAS	Protein subfamily of small GTPases involved in cellular signal transduction
RBC	Red blood cell
RNA	Ribonucleic acid
SAE	Serious Adverse Event
SAP	Statistical Analysis Plan
SD	Stable disease
SH2	Src homology 2
SLL	Small lymphocytic lymphoma
SmPC	Summary of Product Characteristics
SPD	Sum of the products
T _{1/2}	Terminal elimination half-life
TAMs	Tumor-associated macrophages
TEAE	Treatment-emergent adverse events
TRAP-6	Thrombin receptor activating peptide-6
ULN	Upper limit of normal

Abbreviation	Definition
US/USA	United States of America
USPI	United States Package Insert
UV	Ultraviolet
VZV	Varicella zoster virus
WCBP	Women of child-bearing potential

